10.1.1. Clinical Efficacy Measures

The clinical efficacy endpoint of this study is to determine the TTP for each patient.

The primary method used for objective progressive disease is determined by RECIST 1.1 (see [Attachment 8](#)), but is also assessed by mRECIST (RECIST modified for HCC) (see [Attachment 15](#)).

Please note: The mRECIST assessments should be performed according to the guidelines recommended by the American Association for the Study of Liver Diseases-Journal of the National Cancer Institute, AASLD-JNCI (Lencioni and Lovett 2010).

Each patient will be assessed by 1 or more of the following radiologic tests for tumor measurement at the times specified in the Study Schedule ([Attachment 1](#)): CT scan or MRI. In addition, for final study report analyses, a central review of all radiographic examinations will be conducted, and assessments of progression will be based on RECIST 1.1 and if applicable mRECIST.

Other clinical efficacy measures include other time-to-event variables and also RRs that will be determined by both RECIST 1.1 and mRECIST; although, the primary method will be RECIST 1.1.

Radiological assessments will be collected at the times shown in the Study Schedule. MRI and/or CT scans will be collected and stored centrally; if necessary, independent review of all or a representative sample of scans may be considered following study completion.

Changes in biomarkers' (collected as specified in the schedule of events and detailed in [Section 10.3.3](#)) response are measures of progressive disease response, and the relationship to clinical efficacy measures will be explored. These biomarkers are further defined in [Section 12.2.3](#).

Health Outcome/Quality of Life Measures

The assessment of PROs, including disease-specific symptoms and health-related quality of life (HRQoL), will be assessed using the FACT-Hep ([Attachment 10](#)).

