12.2.8. Clinical Efficacy Analyses

Kaplan-Meier analysis will be performed on the observed distribution of TTP (Kaplan and Meier 1958) for each dose in Part A, Part B, Part C, Part D and Part E, with parameter estimates of the TTP median and quartiles being reported. All parameter estimates will be quoted together with their 90% confidence limits. The hazard ratio between the observed TTP distributions of each cohort in Part A will be estimated, recognizing that since 1 dose cohort did not enroll to its full

complement, the precision of the HR will be lower than originally planned. The hazard ratios between the 300 mg/day cohort in Part A and Part B cohort will also be estimated. In addition, the hazard ratio between a subgroup of sorafenib-naïve patients in Parts A and B and patients in Part C may be estimated. The interpretation of any estimate will be considered in light of the size of this subgroup.

Alternative distributions of TTP times, such as exponential Weibull (estimating a shape parameter may also be considered) where median TTP and its 90% CIs will be reported. Individual parameters, such as TTP rate after specific time points (for example, after 12 months on treatment) will be estimated from the TTP distribution.

Secondary efficacy measures include other time-to-event parameters, and these will follow the same analyses as described above.

The overall response rate (ORR) for each cohort in Part A, Part B, Part C, Part D and Part E will be estimated by dividing the total number of confirmed responders by the number of patients who received at least 1 dose of study treatment. The clinical benefit rate will be estimated for each treatment group by dividing the total number of patients experiencing benefit by the number of patients who received at least 1 dose of study treatment. A patient is considered to have received benefit if they achieve a confirmed response, CR or PR, or SD per RECIST v1.1 or mRECIST. Both mean and exact confidence limits will be provided for each group (Cohort 1 and Cohort 2 in Part A, Part B, Part C, Part D and Part E, as well as estimates of differences between 2 cohorts in Part A, between Parts A and B at 300 mg/day, and between sorafenib-naïve patients in Part A and Part B with those in Part C. The interpretation of any estimate in the latter comparison will be considered in light of the size of this subgroup.

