4.2. Secondary Objectives

The secondary objectives of the study are as follows:

- To evaluate the safety of LY2157299 as monotherapy and in combination with sorafenib in HCC patients
- To evaluate the population pharmacokinetics (PK) of LY2157299 as monotherapy and in combination with sorafenib
- To recommend which doses of LY2157299 as monotherapy and in combination with sorafenib to use in future trials recruiting HCC patients
- To characterize other time-to-event distributions, such as progression-free survival (PFS, based on Response Evaluation Criteria in Solid Tumors [RECIST] 1.1 and modified RECIST [mRECIST], for HCC) and overall survival (OS)
- To estimate antitumor efficacy using response rate (RR, based on RECIST 1.1 and mRECIST, for HCC)
- To assess patient-reported outcome (PRO) measures of disease-specific symptoms and health-related quality of life (Functional Assessment of Cancer Therapy Hepatobiliary [FACT-Hep])
- To explore E-cadherin, pSMAD, and β -integrin (and other markers associated with epithelial-to-mesenchymal transition (EMT) transformation and the TGF- β -associated signaling pathway) presence in the original diagnostic tumor tissue and optional posttreatment tumor tissue and the correlation of this with both clinical efficacy endpoints and biomarker response
- To explore the utility of exploratory imaging techniques (for example, positron emission tomography [PET] scan, contrast echography) to assess treatment effect with LY2157299 as monotherapy and in combination with sorafenib when possible
- To explore fibrosis-related biomarkers, such as Fibrotest

5. A Priori Statistical Methods

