5.1. Endpoint Definitions

5.1.1. Clinical Efficacy Endpoints

The primary efficacy endpoint for this study is time to tumor progression (TTP). Secondary efficacy endpoints include progression-free survival (PFS), overall survival (OS), duration of tumor response (DR), time to treatment failure (TTF), overall response rate (ORR) and clinical benefit rate.

A central review of all radiographic examinations will be conducted. Response will be determined by both RECIST 1.1 and mRECIST; although, the primary method will be RECIST 1.1. Best response is determined from the sequence of cycle responses assessed. For complete response (CR) or partial response (PR), best response must be confirmed. A second assessment should be performed ≥ 28 days but no longer than 42 days after the first documentation of response. Two objective status determinations of CR before progression are required for a best response of CR. Two determinations of PR or better before progression, but not qualifying for a CR, are required for a best response of PR. All lesions must be assessed by the same method as at baseline to qualify for response.

All patients will be followed for progression and OS. Patients who come off therapy due to objective progressive disease will be followed for survival every 2 months. From Amendment (b), patients that are clinically asymptomatic may continue on study treatment even if they have objective progression. These patients will then be discontinued from study treatment because of overall symptomatic deterioration, worsening of biomarker results, or other causes. The date of objective progression and date of overall symptomatic deterioration will be collected on CRF. The time to tumor progression, progression free survival, and response rate will be estimated up to the date of objective progressive disease.

Patients who come off therapy and do not have objective progressive disease should be followed every 2 months after discontinuation from study treatment until objective progressive disease is determined (using the same radiological scans as at baseline) or death. Patients who progress should then be followed for survival every 2 months, even if a patient starts a new anticancer therapy. The start date of any new anticancer therapy (occurring during the 30-day poststudy drug discontinuation period or during the long-term follow-up period) will be collected.

The definitions for efficacy endpoints are as follows:

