- **Overall response rate (ORR)** is the percentage of patients who achieved a best overall response of either complete response (CR) or partial response (PR). The overall response rate for each dose cohort will be estimated by dividing the total number of confirmed responders by the number of patients who received at least 1 dose of study drug.
- **Clinical benefit rate** is the percentage of patients who received benefit of a confirmed response, PR, or SD per RECIST 1.1 and mRECIST. The clinical benefit rate for each dose cohort will be estimated by dividing the total number of patients experiencing benefit by the number of patients who received at least 1 dose of study drug.

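### Clinical benefit is met under RECIST 1.1 *or* mRECIST in the protocol but under RECIST 1.1 *and* mRECIST in the SAP, and the protocol's literal rule conflicts with RECIST 1.1 as the primary method

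*SAP*

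**What the plan says.** Protocol 12.2.8 defines benefit patient by patient. A patient has benefited on achieving a "confirmed response, CR or PR, or SD per RECIST v1.1 or mRECIST". The number of such patients is divided by the number who received at least one dose.

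SAP 5.1.1 defines the same endpoint as one percentage, over the same denominator, of patients with a "confirmed response, PR, or SD per RECIST 1.1 and mRECIST".

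Both documents also say which criterion leads. SAP 5.1.1: "Response will be determined by both RECIST 1.1 and mRECIST; although, the primary method will be RECIST 1.1". Protocol 10.1.1, on response rates: "RRs that will be determined by both RECIST 1.1 and mRECIST; although, the primary method will be RECIST 1.1". Protocol 12.2.2 likewise names RECIST 1.1 as the primary method for judging progression when clinical response is determined.

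SAP 5.1.1 lists the clinical benefit rate among the secondary efficacy endpoints. SAP 5.3.8.1 plans 90% exact confidence intervals for it, with chi-squared tests, odds ratios and p-values between cohorts. SAP 5.3.2 lists it among the efficacy measures for the second interim analysis of Part A.

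**The concern.** Programmed as written, the two definitions need not give the same number. The protocol's connective makes either criterion sufficient. The SAP's connective can be read as requiring both, or as asking for one rate per criterion. Neither document says outright which is meant.

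The protocol's version is the more troublesome. It credits a patient whose disease has progressed by the primary criterion, provided mRECIST shows at least stable disease. The same patient is a progression for the TTP analysis by RECIST 1.1 and a success for clinical benefit.

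The trial is open-label and its groups are small. If the rule is not fixed, it can be chosen after the results are seen, and the between-cohort estimates depend on that choice.

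**Working it through.** Neither document states a figure for the clinical benefit rate or for agreement between the two criteria, so there is no published number to reproduce. The check is to see what each wording counts, and then how far the results can separate.

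**What each reading counts.** Classify each patient by benefit (yes or no) under each criterion:

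- *a*: benefit by both
- *b*: benefit by RECIST 1.1 only
- *c*: benefit by mRECIST only
- *d*: benefit by neither, with n = a + b + c + d

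The candidate rates are:

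- Either criterion (protocol, literal): (a + b + c)/n
- Both criteria (SAP, literal): a/n
- RECIST 1.1 alone (the stated primary method): (a + b)/n
- mRECIST alone: (a + c)/n

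Hence:

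- either minus both = (b + c)/n, the share of patients classified differently. This holds whatever the marginal rates and however the disagreement splits.
- either minus RECIST 1.1 alone = c/n, the patients who count only because of mRECIST.

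**Inputs.** n = 40 for Part B (Protocol 7.1). The share classified differently is an assumption, taken as 5%, 10%, 20% and 30%. To turn gaps into rates I also assume 60% benefit (24/40) under each criterion, with disagreement split evenly (b = c). Then a = 24 − b, so the either rate is (24 + b)/40 and the both rate is (24 − b)/40. Intervals are 90% exact (Clopper-Pearson), the confidence level and type the SAP plans.

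| Classified differently | Either criterion | Both criteria | Gap (patients) |
|---|---|---|---|
| 0 (0%) | 24/40 = 60.0% (45.8 to 73.1) | 24/40 = 60.0% (45.8 to 73.1) | 0 |
| 2 (5%) | 25/40 = 62.5% (48.3 to 75.3) | 23/40 = 57.5% (43.3 to 70.8) | 2 |
| 4 (10%) | 26/40 = 65.0% (50.8 to 77.4) | 22/40 = 55.0% (40.9 to 68.5) | 4 |
| 8 (20%) | 28/40 = 70.0% (56.0 to 81.7) | 20/40 = 50.0% (36.1 to 63.9) | 8 |
| 12 (30%) | 30/40 = 75.0% (61.3 to 85.8) | 18/40 = 45.0% (31.5 to 59.1) | 12 |

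In these rows the rate by RECIST 1.1 alone stays at 24/40. The protocol's literal rule exceeds it by c = 1, 2, 4 and 6 patients at 5%, 10%, 20% and 30%. If all the disagreement ran towards mRECIST (b = 0), the excess would be the whole gap.

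**The case against.** The strongest reply is that the SAP is not really in conflict with itself. It elsewhere joins the two criteria with *and* to mean that each is reported, as in the secondary objective on response rate: "RR, based on RECIST 1.1 and mRECIST, for HCC". Nobody would take that to require response by both criteria in one patient. Read with the primary-method sentence in the same section, the SAP then gives two clinical benefit rates with RECIST 1.1 leading. This stands: a reader might infer that the SAP imposes a both-criteria rule, but that is only its literal wording and the less natural reading. Still, the SAP defines a single percentage. Where two versions of an endpoint are wanted, as for PFS with and without clinical progressions, the documents say so.

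The protocol's *or* might likewise mean whichever criterion is being applied. That is possible but harder to sustain, because the sentence says when an individual patient has benefited. If two rates were intended, the sentence needs changing anyway.

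A reader might also infer that the two criteria are known to disagree widely in HCC, citing the 46-patient brivanib study in Protocol Table JBAK.1. The documents do not support this. Those rows compare mWHO with mRECIST, not RECIST 1.1 with mRECIST. The readers differ between rows, and neither stable disease nor clinical benefit is reported. Nor is it useful to argue from the mathematical extremes, in which the two rules could differ by the whole cohort: that would need every patient to be classified oppositely on the same tumours.

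Finally, one rule applied to every cohort favours none by design. That also stands, and no directional bias in the comparisons is shown. The SAP supplied follows Amendment (c) and the protocol is Amendment (e), so a later SAP may have settled the wording. Between the documents supplied, it is unsettled.

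**Conclusion.** The point holds in a limited form. The protocol and SAP word the same secondary endpoint differently, and the protocol's literal rule counts patients who have progressed by the criterion both documents call primary. The SAP is ambiguous rather than clearly wrong.

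The gap between the either and both rules equals the proportion of patients classified differently. On an assumed 5% to 30% that is 2 to 12 of 40 patients in Part B. The range is an assumption throughout, and the 60% benefit rate and even split are used only to show percentages. At 20%, the same data would read as 70.0% or 50.0%.

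The consequence is modest. The endpoint is secondary, SAP 5.3.3 plans no formal efficacy test based on a power calculation, and no decision rule at the final analysis uses this rate. It is worth correcting because the rate will be reported with intervals and p-values.

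**What to change.** Use one definition in Protocol 12.2.8 and SAP 5.1.1: the clinical benefit rate is the proportion of patients who received at least one dose and whose best response by RECIST 1.1 is confirmed CR, confirmed PR, or SD as already defined in Protocol 12.2.2. Report the same rate by mRECIST separately, labelled supportive. State that the criteria are not combined within a patient. Name CR explicitly in the SAP sentence; it is already covered by confirmed response, so that part is editorial.

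Protocol 10.1.1 foresees mRECIST at central review only where applicable, so give the number of patients with an mRECIST reading beside that rate. If a clinical benefit rate has already been reported, for example from the second interim analysis, state in the study report which rule produced it.

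The cost is a sentence in each document and one extra table row per cohort. Assessment by both criteria is already planned, so no new data are needed.

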5.1.2. Health Outcomes Endpoints

The assessment of patient-reported outcomes, including disease-specific symptoms and health-related quality of life (HRQoL) will be assessed using the FACT-Hep questionnaire. The FACT-Hep consists of 45 items in five subscales: (1) physical well-being (PWB); (2) social and family well-being (SFWB); (3) emotional well-being (EWB); (4) functional well-being (FWB); and (5) the hepatobiliary cancer subscale (HCS) to assess health related quality of life in patients with liver cancers. The 27 item FACT-G total score include PWB, SFWB, EWB and FWB of FACT-Hep to assess the general HRQoL and the 18 item HepCS to assess disease specific issues (specifically on hepatobiliary).

FACT-Hep total, FACT-Hep subscales scores, trial-outcome index (TOI), NCCN-FACT-Hepatobiliary Symptom Index 18 [NFHSI-18]), NFHSI-18 subscale scores and individual symptoms from HCS subscale will be assessed.

Scoring the FACT-G:

Scoring for the FACT-Hep will follow the guidelines and algorithms developed by the FACIT (Functional Assessment of Chronic Illness Therapy) group (<http://www.facit.org/>).

Negatively stated items in the FACT-G are reversed by subtracting the response from “4” before being added to obtain the subscale totals.

For the following items, compute individual item score by subtracting each item response from “4”.

- Physical well-being (PWB): items GP1 to GP7
- Emotional well-being (EWB): items GE1, GE3 to GE6
- Hepatobiliary cancer subscale (HCS): items C1, C2, C5, Hep1, Cns7, Cx6, HI7, Hep2 to Hep6, HN2, Hep8

A subscale score is the sum of individual item scores after reversing for the selected items above and it is calculated as follows:

$$\text{Subscale score} = [\text{Sum of item scores}] \times [\text{N of items in subscale}] \div [\text{N of items answered}]$$

The subscale scores are prorated if there are missing items in the subscale. This is acceptable as long as 50% of the items in each subscale were answered (eg. a minimum of 4 out of 7 items, 4 out of 6 items etc). Number of items in each subscale are as follows: 7 items in PWB, SWB, FWB; 6 items in EWB; and 18 items in HCS. The range of each subscale score are as follows: PWB: 0 – 28; SWB: 0 – 28; EWB: 0 – 24; FWB: 0 – 28 and HCS: 0 – 72.

The total scores (TOI, FACT-G, FACT-Hep and NFHSI-18) are summation of the component subscales scores.

The FACT-G total score (score range: 0 – 108) is the sum of the un-weighted subscale scores of PWB, SWB, EWB and FWB. Response rate for the FACT-G has to be greater than 80% (at least 22 out of 27 items completed) for it to be acceptable indicator of patient’s quality of life.

The FACT-Hep total score (score range: 0 – 180) is the sum of the un-weighted subscale scores of PWB, SWB, EWB, FWB and HCS.

The FACT-Hep trial-outcome index (TOI) (score range: 0 – 128) is the sum of the un-weighted subscale scores of PWB, FWB and HCS.

See SAP Attachment 1 for FACT-Hep Scoring Guidelines for the above scores.

The NFHSI-18 total scale score consider 18 symptoms (score range: 0-72) in FACT-Hep and is calculated by summing GP1, GP2, GP3, GP4, GP5, GP6, AN7, GE1, GE6, GF3, GF5, GF7, C2, C6, CNS7, HI7, Hep2, and Hep8. The subscale scores of NFHSI-18 consists of NFHSI-DRS-14 (disease related symptoms; score range: 0-56), NFHSI-FWB-3 (functional well-being; score range: 0-12) and NFHSI-TSE-1 (treatment side effects; score range 0-4). See SAP Attachment 2 for guidelines on scoring of NCCN/FACT Hepatobiliary Symptom Index-18 and the subscales.

The higher the scores the better the quality of life.

5.1.3. Pharmacodynamic Efficacy Endpoints

Elevated AFP is a marker of disease progression in HCC patients. Hence, a treatment effect can be measured by following the kinetics of AFP reduction during the treatment period and a sustained reduction of 50% over 3 months is a relevant change suggesting a treatment effect.

Other AFP response criteria will be studied including the following definition : AFP response is >20% decrease in AFP from baseline (samples collected closest to first dose) during 8 weeks of treatment.

Elevated TGF- β 1 (possibly adjusted for PF4 level), though less validated, correlated with poor clinical outcome in HCC patients. Hence, a reduction in TGF- β 1 levels is another marker of activity of a beneficial treatment effect.

The protein, E-cadherin, is associated with EMT and elevated levels of this marker is found in aggressively growing HCC. Hence, a change in kinetics of its level may reflect treatment effect.

Additional PD endpoints (for example, Fibrotest, T-cells counts, AFP L3, PIVKII) may be considered for analysis.

5.1.4. Safety Endpoints

Safety measures that will be used in the study include hematology, chemistry, urinalysis, vital signs, adverse events (AE), serious adverse events (SAE), treatment-emergent adverse events (TEAE), electrocardiogram (ECG), echocardiogram, dose adjustments and omissions, and blood transfusions. All safety summaries and analyses will be based upon the safety population as defined in Section 5.2. All adverse events will be mapped to MedDRA (Medical Dictionary for Regulatory Activities) LLT (Lowest Level Term) and graded using the National Cancer Institute Common Terminology Criteria for Adverse Events (NCI CTCAE) version 4.0.

5.2. Analysis Sets

Efficacy and safety analyses will be based on all enrolled patients receiving at least one dose of LY2157299.

Pharmacokinetic (PK) analysis will be conducted on patients who received at least one dose of study drug and have had samples collected.

Pharmacodynamic (PD) analysis will be conducted on patients who have received at least one dose of the study drug and have had samples collected.

Pharmacogenomic analysis will be conducted on patients from whom a valid assay result has been obtained from whole blood and serum, and tumor tissue blocks from diagnostic or surgical tumor samples.

5.3. Statistical Methods

5.3.1. Design Considerations

Study JBAK is a multicenter, randomized trial characterizing the TTP distribution of study treatment in Child-Pugh Class A or B HCC patients.

Starting with Amendment (c), there may be 3 parts to this study: Child-Pugh A and B7 patients are enrolled in Part A and Part B; Parts A and B are distinguished based on baseline AFP levels (Figure JBAK.5.1.). In Part C, patients with no prior systemic treatment will receive LY2157299 (160 or 300 mg/day) in combination with sorafenib 400 mg BID.

A maximum of 190 patients will be enrolled into the study: 109 into Part A, 40 into Part B, and approximately 40 into Part C. Given these changes, the primary objective of this study is to characterize both the TTP distributions and the effect on TGF-β-associated serum biomarkers (for example, TGF-β, AFP, E-cadherin) of study treatment in patients with HCC.

In Part A, patients with AFP ≥1.5 ULN will be randomized to 2 cohorts based on initial dose of LY2157299 to be received (160 or 300 mg/day). Eligible patients will be randomized through interactive voice response system (IVRS) after completing screening at Visit 0 into 1 of these cohorts (the 2 cohorts being balanced as far as possible through IVRS using minimization methods for AFP levels, etiology, and whether sorafenib naïve or not) and will receive LY2157299 for 14 days followed by 14 days of rest.

In Part B, patients with normal AFP (<1.5 ULN) will receive LY2157299 300 mg/day for 14 days followed by 14 days of rest. Patients who have a normal AFP level and who meet all criteria for enrollment will be assigned by the IVRS to receive the LY2157299 300-mg/day dose after completing the screening at Visit 0.

[figure not shown]

Figure JBAK.5.1. Illustration of study design for Protocol H9H-MC-JBAK Part A and Part B

Part C will evaluate LY2157299 in combination with sorafenib in patients with advanced HCC and Child-Pugh A status who have not received previous systemic treatment. Patients who have not received prior systemic treatment and who meet all criteria for enrollment will be assigned by the IVRS to receive either the LY2157299 80 mg BID or the LY2157299 150-mg BID dose after completing the screening at Visit 0. Up to 40 patients may be enrolled.

Part C comprises a safety lead-in of 2 cohorts followed by an expansion phase with selected safe dose(s) (Figure JBAK.5.2.). Patients enrolled in Cohort 1 will be administered LY2157299 80 mg BID on Days 1 to 14 in combination with sorafenib at 400 mg BID on Days 1 to 28 on a 28-day cycle. Three patients will be enrolled on Cohort 1; if no dose-limiting toxicities (DLTs) (related to LY2157299 or combination regimen) are observed in Cycle 1, 3 patients will be treated on Cohort 2 at LY2157299 150 mg BID on Days 1 to 14 in combination with sorafenib at 400 mg BID on Days 1 to 28 on a 28-day cycle. If a DLT related to LY2157299 or combination regimen is observed in either cohort in the first 3 patients in Cycle 1, then that cohort will be expanded to include additional 3 patients. Six to 12 patients may be enrolled in the safety lead-in, depending on the observed DLTs. PK sampling will be conducted in Cycle 1 with the intent to assess drug-drug interactions between LY2157299 and sorafenib.

Depending on the results from the safety lead-in cohorts and analysis from Parts A and B, the expansion cohort will consist of 1 of the following:

- Single treatment group: LY2157299 80 mg BID on Days 1 to 14 in combination with sorafenib at 400 mg BID on Days 1 to 28 on a 28-day cycle, or
- Single treatment group: LY2157299 150 mg BID on Days 1 to 14 in combination with sorafenib at 400 mg BID on Days 1 to 28 on a 28-day cycle, or
- Two treatment groups: LY2157299 80 mg BID on Days 1 to 14 in combination with sorafenib at 400 mg BID on Days 1 to 28 versus LY2157299 150 mg BID on Days 1 to 14 in combination with sorafenib at 400 mg BID on Days 1 to 28. Both cohorts being on a 28-day cycle.

Patients enrolled in the safety lead-in cohorts may continue treatment as per that cohort.

[figure not shown]

Figure JBAK.5.2. Illustration of study design for Protocol H9H-MC-JBAK Part C.

Dose escalation will be driven by safety using the 3+3 method. Both cohorts will have a minimum of 3 patients enrolled into it. If 1 patient in either dose level experiences a DLT within the first cycle of LY2157299 and sorafenib, then up to 3 additional patients will be enrolled at that dose level. If a DLT is observed in 2 or more patients at either dose level in the first cycle, dose escalation will cease and either the previous dose level will be declared the MTD or, following discussions between the sponsor and investigators, additional patients may be treated at intermediate doses between the previous and current dose levels.

One cycle is defined as 28 days (a minimum of 26 days and a maximum of 31 days: the treatment period must be a minimum of 10 days and a maximum of 14 days; the “off-treatment” period can vary to ensure an overall cycle length of 26 to 31 days). In extenuating circumstances, the “on study drug” window for LY2157299 is allowable from Day 10 to Day 14. (In Part C safety lead-in in Cycle 1, patients must have received 14 days of LY2157299 treatment). If patients are not evaluable for safety and/or PK in Cycle 1 of Part C safety lead-in, the patients will be replaced.

The planned treatment duration is 6 cycles, but patients may continue to receive study drug if they are still benefiting from treatment in the opinion of the investigator and Lilly physician.

In case of occurrence of severe toxicities in later cycles in patients being treated with either LY2157299 monotherapy or with LY2157299 in combination with sorafenib, the sponsor will review and choose a lower dose, if necessary.

This Phase 2 study will be considered complete once 85% of events for survival analysis in Part C have occurred. Patients still on treatment at the time that the study is considered complete, may enter the treatment extension period and continue to the study treatment.

